IRB oversight and approval will be based on 45CFR 46 HHS criteria. We anticipate our study will be determined to be no more than "minimal risk". The M-MILK intervention's safety has been demonstrated in infants as young as 22 weeks GA. According to the M-MILK protocol, nurses or parents will carefully observe infants' cues and responses during the M-MILK intervention and stop the administration if infants do not engage or exhibit any signs of distress. Thus, there is minimal risk associated with this protocol. Every effort will be made to minimize the risks. There may be risks associated with administration of M-MILK and collecting buccal swab samples including gagging and minor discomfort. Of note, these risks are no more expected risks to infants than what they might experience during a typical day, routine oral care, or feeding. Nurses will document infants' responses or any unexpected and serious adverse events to M-MILK intervention in the M-MILK Documentation paper sheet. A research nurse will review the documentation and report to PI if there are any unexpected and serious adverse events. For the NAPI assessment, we will perform maneuvers such as partially removing swaddle blanket, gentle stretching/bending of arms and legs, gently picking up, and stimulating vision and hearing with soft rattle sounds and talking voices. These maneuvers may pose minimal risks such as feeling cold, and mild discomfort due to stretching/bending/picking up, or noises. Of note, these risks are no more expected risks to infants than what they might experience during a typical day, routine care, or physical exam. Additionally, this research also carries a minimal risk of loss of data confidentiality/security. We also recognize that there are unique risks related to loss of confidentiality regarding a participant's epigenetic and microbiome data; however, we consider this risk to be rare.

b. Adequacy of Protection Against Risks

i. Informed Consent and Assent

The potential risks will be presented to the parents prior to enrollment. If parents are interested in having their preterm infants participate in the study, written informed consent will be obtained. Alternatively, the potential preterm infant will receive standard care if the parents choose to not enroll in the study. Premature infants, by virtue of their age cannot give consent or assent and therefore will not give assent or participate in the informed consent process.

ii. Protections Against Risk

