Risks associated with loss of electronic data confidentiality/security will be mitigated through the utilization of secure electronic database (REDCap) and research network drive process to ensure that only authorized research personnel have access to the research data. The original signed informed consent documents will be kept in a locked cabinet at LUC CTRE. All infants will be assigned a study ID number. All of the data will be identified only by a study ID number. All discussions of specific research participants in our research team meetings will use this number rather than names. Electronic data will be encrypted with a password known and viewed only to the research staff. The password will be changed every six months.

The M-MILK Documentation paper sheets will have the infant's name on it and is available at the infant's bedside for nurses to document M-MILK. The completed sheets will be collected daily by a NICU charge nurse and stored in a locked cabinet on the unit. A research team member will pick up the completed sheets daily, and stored them in a locked cabinet in at LUC CTRE (Maywood, IL) for data entry. Upon completion of data entry into REDCap, the completed sheets will be shredded immediately.

Buccal swab and fecal samples will be labeled only with study ID numbers and collection date, and stored in a locked cabinet in a locked laboratory at LUC CTRE (Maywood, IL). We will securely transport buccal swab and fecal samples to Rush (Chicago, IL) using biosafety transfer containers and via car.

Video recordings will be downloaded and stored on a secure research network drive, hosted by LUC. Infant's and parent's face will be visible in the videos as we need to observe their interactions and infant's feeding skills. However, we will not include any identifiers such as name or date in the videos. The video files will be labeled only with study ID numbers and recorded date.

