De-identifiable data will be shared with University of Illinois at Chicago Research Informatics Core. All data; e.g., raw sequence data, processed data and sample mapping; will be transmitted between systems via encrypted transport protocols, i.e. HTTPS or SFTP. All desktop and laptop computers are protected by strong password authentication with whole disk encryption enabled. Remote servers are protected by network firewalls, intrusion detection software, and either bastions or two factor authentication for any remote logins. Any passwords on the remote systems are subject to strong password requirements, i.e., minimum password length, combinations of different character types (capital letters, lowercase letters, numbers, special characters), and are not typical English words.

Biospecimens are materials that come from infants that may include blood, tissue, urine, bone marrow, saliva, cells, etc. In this study, we will collect cheek tissue and stool. Most biospecimens contain DNA. We will not use biospecimens collected as a part of this study for whole genome sequencing. However, we will use biospecimens collected as a part of this study to sequence a short portion of the genes of interest that starts gene transcription found at the beginning of the genes. The de-identified sequence data will be submitted to online government data repositories per National Institute of Health requirements. All the sources of the sample are de-identified and infants' individual identity will not be revealed.

De-identified data, photos and/or selected brief segments of videos from this study may be shared with others for research/educational purposes in reports, scientific papers, research/educational meetings, and/or research/educational websites. De-identified data, photos and/or selected brief segments of videos from this study may also be shared on research/educational social media platforms. We will remove or code any personal identifiable information that could identify participants before data are shared with other researchers to ensure that no one will be able to identify participants from the information we share. De-identified data, the photos and/or selected brief segments of videos will be stored indefinitely. Informed consents and video recordings will be securely shredded/deleted after all related data are published or up to 5 years. Buccal swab and fecal samples will be stored and securely destroyed after all related data are published or up to 5 years.

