Strict confidentiality of data files will be maintained. Data management will be facilitated using REDCap. SAS (v 9.4) will be used for all statistical procedures and analyses. Levels of missingness, variable distributions, and outliers will be examined throughout data collection for quality assurance as well as prior to statistical modeling. We will calculate descriptive statistics for all variables of interest to describe the variability of study variables, and conduct sample size estimation for the planned R01 application. Comparisons will be made using an intent-to-treat approach with participants analyzed in the groups to which they were randomized. Feasibility will be assessed with respect to enrollment, adherence, acceptability, and safety. We will calculate the percentage of infants who (1) were eligible, approached, consented, enrolled, and randomized over the recruitment period, (2) were retained for the duration of the study, (3) completed all inpatient data collection, and (4) completed post-discharge follow-ups. To determine the adherence of M-MILK, we will calculate the daily numbers of completed M-MILK and the daily numbers of expected M-MILK implementation (numbers of hands-on care episodes before full gavage feedings) to obtain the daily percentage of M-MILK completion. We will summarize findings from M-MILK Acceptability Questionnaire by nurses and parents. We will also summarize findings from M-MILK EPIC charting regarding infant's responses and any adverse events to monitor for the safety of M-MILK.

X. Study Timeline

Table 2. The proposed pilot study will require 1 year to complete. During the first 3 months, we will hire and train the team members. We anticipate enrolling 2 infants per month for 9 months. An additional 3 months will be required to complete the intervention and collect study data. Data entry and analyses will be ongoing. We will spend 6 months to complete data analyses. An additional 6 months will be needed to prepare the final report and disseminations.

Table 2. Study Timeline

Activity/Month	Month 1-3	Month 3-12	Month 12-15	Month 15-21	Month 21-27
Preparation & Staff Training	X				
Recruitment & Enrollment		X			
Data Collection		X	X		
Data Entry & Analyses		X	X	X	
Final Reports & Dissemination				X	X

XIII. Literature Cited

1. Barfield WD. Public Health Implications of Very Preterm Birth. *Clin Perinatol*. Sep 2018;45(3):565-577.

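### Adverse-event capture is described only for M-MILK delivery, with no by-arm tabulation, mismatched recording and summary sources, and paper shredded straight after entry

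*Combined protocol and SAP*

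**What the plan says.** - **Role of safety.** Section IX: "Feasibility will be assessed with respect to enrollment, adherence, acceptability, and safety". Section IV sets thresholds for implementation, recruitment and retention, but none for safety.
- **Recording.** Section VIII.a has nurses write down how infants respond, or "any unexpected and serious adverse events to M-MILK intervention in the M-MILK Documentation paper sheet". Escalation follows: "A research nurse will review the documentation and report to PI if there are any unexpected and serious adverse events".
- **The sheet.** Section VIII.b.ii.2 describes it as carrying the infant's name and being "available at the infant's bedside for nurses to document M-MILK". Then: "Upon completion of data entry into REDCap, the completed sheets will be shredded immediately".
- **Summary source.** Section IX: "We will also summarize findings from M-MILK EPIC charting regarding" infant responses and adverse events.
- **Other identifying material.** Section VIII.b.ii.2: "Informed consents and video recordings will be securely shredded/deleted after all related data are published or up to 5 years".
- **Removal.** Section VII.a.ii reclassifies an enrolled infant who later develops an exclusion criterion as a screen failure and excludes the infant. Necrotizing enterocolitis is on that list. Section VIII.b.ii.1 removes infants who become unstable or gain a new diagnosis and no longer meet the inclusion criteria. Section IX states an intent-to-treat approach.
- **Data on all infants.** Table 1 and the Procedures text after it collect diagnoses, therapies, weight gain and daily stressor scores from EPIC in both groups.

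**The concern.** Infants born at 22 to 33 weeks have frequent serious events from prematurity alone. An event reaches the sheet only if someone at the bedside judges it to be a reaction to M-MILK, and Section VII.a.iv says staff nurses cannot be blinded. A list built that way mixes the effect of the intervention with the judgement of people who know the allocation. It also leaves the randomised control group out of the safety account.

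Two further weaknesses add to this. An event on paper need not appear in the EPIC charting that feeds the summary. Once the sheet is gone, a disagreement between REDCap and EPIC cannot be settled by going back to it. The same sheet holds the nurse-documented administrations, so the nurse-recorded part of the 90% implementation criterion loses its paper source as well.

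At stake is whether the pilot hands the planned R01 a complete, traceable set of safety counts in both arms.

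**Working it through.** The plan gives no safety figure to reproduce, so the check sets the sections side by side.

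1. **Where an event goes.** Section VIII.a: bedside nurse to paper sheet, then research-nurse review, then report to the investigator. Section VIII.b.ii.2: paper sheet to REDCap, then shredded.
2. **Where the summary comes from.** Section IX: EPIC charting. No section says that events on the sheet are transcribed into EPIC; the Procedures text mentions only an EPIC order for M-MILK. The scope differs too: unexpected and serious events on the sheet, any adverse event in the EPIC summary. No reconciliation is described.
3. **Which arm is covered.** The sheet exists to document M-MILK, and the charting is labelled as M-MILK charting. That both cover only the M-MILK arm is inferred from their purpose; the documents do not say so. No adverse-event definition, control-arm form or by-arm safety table appears anywhere.
4. **Who can drop out.** An infant who develops necrotizing enterocolitis is excluded under Section VII.a.ii. If that infant's data leave the analysis, a central safety event leaves with them. Section IX analyses participants as randomised. The sections do not say which rule governs the safety data.
5. **What is already available.** Diagnoses and therapies are extracted from EPIC for all infants throughout hospitalisation, so a by-arm table needs no new data stream.
6. **What such a table could show.** For k events against 0 with n infants per arm, the two-sided Fisher p-value is 2 × C(n,k) / C(2n,k). The plan gives two arm sizes: 6 (Sections III, VI.a and VI.c) and 10 (the opening summary).
   - n = 6: 4 v 0 gives 2 × 15/495 = 0.061; 5 v 0 gives 2 × 6/792 = 0.015.
   - n = 10: 4 v 0 gives 2 × 210/4845 = 0.087; 5 v 0 gives 2 × 252/15504 = 0.033.

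   At either size p falls below 0.05 only from 5 v 0. The table would therefore be descriptive, and its value lies in completeness and symmetry rather than in testing.

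**The case against.** A reader might infer several stronger conclusions that the documents do not support.

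- **That events are recorded only on paper.** Section IX implies that EPIC also holds adverse events, and the fidelity text in Section VII.a.v has parents record infant responses through the daily link.
- **That safety cannot be compared with controls.** Diagnoses, therapies, weight gain and stressor scores are collected in the same way in both groups, and Section IX plans descriptive statistics for all variables of interest. What is missing is a stated by-arm event table, not the data. Responses to a milk-drop administration have no control counterpart by design, and Section IV lists no comparative safety aim.
- **That the records, or all adherence data, cannot be verified.** The fidelity text provides daily review of nurse documentation, a separate parent record and an in-person audit of 10% of administrations, and the entered data stay in REDCap. What is lost is later checking of entries against the paper.
- **That the wide confidence bound left by zero events in 6 infants measures the defect.** That bound depends on arm size alone and would be the same after every change proposed here.

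It can also be said that shredding is a confidentiality measure, because the sheets carry names, and that it breaks no rule in the plan. That is fair. The retention of consents and videos shows only that locked storage of identifying material is already accepted, not that the sheets must be kept as long.

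After all this, the source mismatch, the attribution-based capture without a by-arm table, the unclear handling of removed infants and the early loss of the paper still stand.

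**Conclusion.** The point holds as a modest, inexpensive improvement to a minimal-risk feasibility pilot. As written, the safety summary would rest on events attributed to M-MILK by unblinded staff. Its stated source differs from where those events are recorded, no by-arm tabulation is planned, and the paper is destroyed without a stated check of the entries. Infants removed for a new diagnosis could also be lost from the safety account.

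The size cannot be expressed as a bias or an event count, because the documents give no adverse-event rates, entry-error rates or safety threshold. The conclusion assumes that the sheet and the EPIC charting cover only the M-MILK arm, and that no separate safety form or data-handling manual supplies the missing steps.

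**What to change.** 1. **Reconcile the sources.** Amend Sections VIII.a and IX to name the sheet/REDCap record and EPIC as joint sources, with the same event scope, and state that they are cross-checked and discrepancies resolved.
2. **Tabulate by randomised arm.** From the EPIC diagnoses and therapies already extracted for all infants, report one fixed list of serious or unexpected events and new diagnoses, regardless of attribution. Use one window for both arms, for example from the later of enrolment and day 3 of life (when M-MILK starts) to NICU discharge. Include infants excluded or removed under Sections VII.a.ii and VIII.b.ii.1, and reconcile those sections with the intent-to-treat statement as far as the data are concerned. Label the table descriptive, with no hypothesis test.
3. **Delay shredding.** Keep the sheets in the existing locked cabinet until the REDCap entries have been verified against them and the database is locked, then shred.

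The cost is a little extra abstraction and longer locked storage of name-bearing sheets. Treatment, assessments and sample size do not change.

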Intervention Training and Fidelity. Delivery of M-MILK by nurses or parents introduces potential threats to intervention fidelity. We will take the following strategies for training and improving intervention fidelity. 1) In-person 1-hour M-MILK training sessions for all nurses, led by the PI and the M-MILK Expert Consultant, held in groups quarterly and individually as needed. The M-MILK training sessions will cover the M-MILK Toolkit. An acceptable attendance rate during the first quarter is 90%. 2) M-MILK Toolkit is available for nurses to view on the M-MILK study website and LUMC HealthStream platform for reference and continue education. 3) Nurses will document infant's responses to M-MILK; and research team will review M-MILK documentation by nurses daily to ensure accuracy and completion. 4) In-person 30-minute M-MILK training sessions for parents in the M-MILK group, within 1 week of enrollment, provided by a Research Nurse. The M-MILK training sessions will cover the M-MILK Toolkit. The M-MILK training sessions for parents are followed by in-person observation and hands-on return demonstration, and questions/answers with a Research Nurse. An acceptable attendance rate for the parent M-MILK training sessions is 90%. 6) M-MILK Toolkit is available on the M-MILK study website for reference and continuing education. 7) Access to the M-MILK content on the website is restricted to nurses and parents in the M-MILK group, thus there will be 2 different access codes for each group. 8) We will request parents not to share the M-MILK content with other parents in the NICU. 9) Parents will document the M-MILK activities and infant's responses via the daily activity link; acceptable completion rate for parent documentation is 85%. 10) Research Nurse will conduct an in-person audit of 10% of the M-MILK administrations by nurses or parents quarterly using M-MILK Intervention Fidelity Checklist; acceptable reliability rate is 90%. 11) The Research Nurse who is responsible for studying main outcome evaluations will be blinded to the infant's group assignment.

2. Attention Control Group

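### Section VIII.a sends an adverse event to the PI only if it is both unexpected and serious, and its recorded category is narrower than the summary planned in Section IX

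*Combined protocol and SAP*

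**What the plan says.** Section VIII.a describes recording and escalation in consecutive sentences. On recording: "Nurses will document infants' responses or any unexpected and serious adverse events to M-MILK intervention in the M-MILK Documentation paper sheet". On escalation: "A research nurse will review the documentation and report to PI if there are any unexpected and serious adverse events". Shortly before these, the section names the reactions it foresees: "There may be risks associated with administration of M-MILK and collecting buccal swab samples including gagging and minor discomfort". It considers them no greater than those of routine care.

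The intervention training and fidelity text in Section VII adds two records without any condition on seriousness or expectedness. For nurses: "Nurses will document infant's responses to M-MILK; and research team will review M-MILK documentation by nurses daily to ensure accuracy and completion". For parents: "Parents will document the M-MILK activities and infant's responses via the daily activity link".

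Section IX lists safety beside enrollment, adherence and acceptability as the components of feasibility, and states the planned output: "We will also summarize findings from M-MILK EPIC charting regarding infant's responses and any adverse events to monitor for the safety of M-MILK".

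**The concern.** Joining the two conditions with *and* makes the escalation rule narrow. Someone applying the sentence as written would not have to tell the PI about a serious event judged to be of an expected type, or about a surprising event that fell short of serious. The first case could arise here because the plan itself lists gagging among the foreseen reactions. If a serious episode began with gagging, the research nurse would have to decide whether it still counted as unexpected. The text available for review defines neither term, lists no expected serious events and gives no reporting timeline.

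The adverse-event category on the paper sheet has the same double condition, while the analysis section promises a summary of all adverse events. If the sheet is the main prospective record, the summary could look cleaner than the infants' actual experience.

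M-MILK starts on day 3 of life, including in infants on mechanical ventilation, and the pilot's safety findings are meant to support a larger trial. The PI should hear of serious events however they are labelled.

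**Working it through.** The plan gives no figure on this point, so the check sets the texts side by side.

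**Step 1: escalation.** Cross the two properties in the rule and ask which events have a stated route to the PI.

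| Event | Rule as literally written | If the rule read *serious or unexpected* |
|---|---|---|
| Serious, unexpected | Reported | Reported |
| Serious, expected | No stated route | Reported |
| Not serious, unexpected | No stated route | Reported |
| Not serious, expected | No stated route | No stated route |

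The literal rule covers 1 of 4 categories and the alternative covers 3 of 4. These are counts of categories, not shares of events.

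**Step 2: other routes to the PI.** Four other places could supply one.
- The daily review in Section VII checks that documentation is accurate and complete. It states no duty to tell the PI about an event.
- The screening procedures in Section VII continue until discharge and exclude an infant who develops an exclusion condition, such as necrotizing enterocolitis. This covers only the listed conditions.
- Risks Related to Study Procedure (Section VIII.b) removes an infant who becomes unstable or gains a new diagnosis and no longer meets the inclusion criteria. A serious event that leaves eligibility unchanged is not covered.
- The same part requires administration to stop at signs of distress. That is a bedside action, not a report.

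None of these gives the middle two rows of the table a route to the PI.

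**Step 3: recording.** The nurse sentence has two branches, infants' responses and adverse events. Only the second has the double condition: "or any unexpected and serious adverse events to M-MILK intervention in the M-MILK Documentation paper sheet". Gagging or distress during M-MILK can therefore be written down as a response by nurses under Sections VII and VIII.a, and by parents through the daily link. No rule says when a response becomes an adverse event, or that it is then marked for seriousness and expectedness.

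**Step 4: recording against analysis.** Section VIII.a names a paper sheet. Risks related to Data Confidentiality (Section VIII.b) has the sheets entered in REDCap and then destroyed. Section IX takes "any adverse events to monitor for the safety of M-MILK" from M-MILK charting in EPIC. The two sections differ in scope (unexpected and serious against any) and in source (paper against EPIC). Table 1 also takes medical diagnoses and therapies from EPIC throughout the stay, so some events could be found there. However, the text describes no adverse-event entry within the EPIC M-MILK charting.

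**Step 5: weight of one event.** Section VI plans 6 infants per group, and the opening summary says 10. One infant with a serious event is 1/6 = 16.7% of the M-MILK arm, or 1/10 = 10%. A single event that is not escalated or not classified can change what the pilot says about safety.

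**The case against.** The strongest reply is that the plan records much more than the double condition suggests. A reader might infer from Section VIII.a that nurses write down nothing except unexpected and serious events, so that every non-serious event is lost. The documents do not support that. The same sentence has nurses document infants' responses, Section VII repeats this without limit, and parents report responses too. A reader might also infer that the summary in Section IX cannot be produced. That does not follow either, because its named source is EPIC charting, and a limit on one record does not empty another.

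Two further replies have some force. *Unexpected and serious adverse events* can be read as meaning both kinds of event, in which case the escalation rule is already wide. And the plan names no expected event that is serious: gagging and minor discomfort are presented as mild, so the serious-but-expected category has no example in the text.

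What stands is that recording is broader than the adverse-event phrase implies, and that the authors may have intended a wider escalation rule. But a recorded response is not a classified adverse event, and a later summary from EPIC does not notify the PI. If two readings of the escalation sentence are possible, staff may follow the narrow one. The lack of a named serious expected event does not help, because the rule leaves that classification to the research nurse without a definition.

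**Conclusion.** The point holds for escalation and, more weakly, for the match between recording and analysis. On its literal wording the plan gives a PI route to one of four categories of adverse event, and no other section provides one for serious events of an expected type or for unexpected events short of serious. The sheet's adverse-event category is narrower than the planned summary, and the two sections name different sources. Capture of the remaining events is therefore not assured, but it is not excluded.

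This rests on reading *and* as requiring both conditions, and on the text available for review, which does not include the sheet itself. Without event rates, neither the share of serious events that would go unescalated nor any delay can be quantified. The plan should be changed because safety is a named feasibility component and the arms are very small. It is a fault in a reporting rule and does not invalidate the trial.

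**What to change.** 1. In Section VIII.a, have the research nurse report to the PI any adverse event that is *serious or unexpected*.
2. In the sentence before it, have nurses document *infants' responses and any adverse events to M-MILK*, with seriousness and expectedness marked for each event. Define both terms so that the marking is consistent.
3. Reconcile Sections VIII.a and IX on the source of the safety summary. Either name the paper sheet as entered in REDCap, or state that adverse events are charted in EPIC and how that relates to the sheet. If both are used, say how they are combined.

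The cost is an edit to two sentences, a clarification in Section IX and two extra items per event on the nurses' record. A few more events will need review and reporting. Keeping the wording tied to events to M-MILK limits the added load in a population with frequent illness.
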